## **5. LAY LANGUAGE SUMMARY OR SYNOPSIS (no more than one paragraph)**

Globally, 41% of all pregnancies are unintended, increasing risk for maternal and infant morbidities and mortality. Most unintended pregnancies occur in the context of contraceptive non-use or failure. Women with husbands not supportive of contraception are more likely to report contraceptive non-use, and women with sexually abusive husbands are more likely to report contraceptive failure. Such findings highlight the need for family planning (FP) interventions that engage both women and men, focus on eliminating marital sexual violence (MSV) and promote use of effective (low failure risk) spacing contraception including long-acting reversible contraception (LARC; e.g. intrauterine device or IUD). Rural India, with some of the lowest rates of contraception and highest rates of marital violence globally, offers an important context in which to test such interventions, with global implications. Prior research from this team documents promise of the original CHARM intervention, a gender equity (GE) FP intervention engaging men and delivered by male health providers over three months. This intervention improved contraceptive use and reduced likelihood of MSV, but demonstrated no reduction in unintended pregnancy; additionally, it demonstrated good participation from men (91%) but less from couples (51%), largely due to women's discomfort with a male provider. Poor reach to women and provision of only short-acting contraceptives (pill, condom) more vulnerable to contraceptive failure, likely compromised unintended pregnancy outcomes. Based on these findings, we propose CHARM2, which will include CHARM sessions for men AND parallel women-focused GE+FP sessions delivered by a female provider and inclusive of broader contraceptive options, including LARC, as well as a combined couples session. This study seeks a) to implement CHARM2, b) to evaluate its impact on contraceptive use, unintended pregnancy, and MSV with rural couples in India, and c) to assess its potential for sustainability in rural India, using implementation science methods. To evaluate the impact of CHARM2 on our outcomes of interest, a two armed cluster randomized controlled trial will be conducted with N=1200 married couples from 20 geographic clusters (n=60 couples per cluster) in rural Maharashtra, India. Participants will receive CHARM2 or the standard of care (SOC) control condition, which will involve community health workers offering pills/condoms and linking women to public health clinics. Outcomes for both intervention and SOC participants will be assessed via pregnancy testing and surveys at baseline and 9 & 18-month follow-ups. Implementation science methods will be used to assess the quality, scalability, and replicability of CHARM2 for uptake by rural health care systems (i.e., sustainability). Specifically, in-depth interviews (IDI) will be conducted with CHARM2 intervention couples (n=50), providers (n=20); 5-7 focus group discussions (FGDs) will be conducted with mother in laws (MILs) of couples that participate in IDIs, and key stakeholders from the family planning and rural health infrastructures at state, national and international levels (n=50), and we will implement a cost-effectiveness analysis of CHARM2.

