**The CHARM2 Intervention:** CHARM2 intervention will involve gender, culture and contextually-tailored FP+GE counseling sessions delivered individually to husbands by a trained male health provider (2 sessions), and, in parallel, delivered individually to wives by a trained female ANM or trained provider/counselor (2 sessions), as well as a combined couples session. CHARM2 differs from the original CHARM intervention by adding parallel sessions for wives, delivered by the ANM, and including LARC counseling for husbands and wives and opportunity for LARC provision in the sessions with women. The ANM or trained provider/counselor session will use GE counseling from the CHARM couple session with public health FP and LARC counseling. Sessions will be provided at the participants' home or within the clinical setting, as the husband and wife prefer. The 5 sessions will be delivered across 3 months with a minimum of 1 week between the men's sessions; the men's Session 1 must be delivered before the female session.

**SOC Control Condition:** Under India's public health system, ASHAs and ANMs provide household visits to women to increase awareness and use of FP services, with ASHAs incentivized to bring women to PHCs for FP services and ANMs rarely providing contraceptives. For those women or couples that reach the PHC, SOC FP counseling and services are delivered by a physician; free contraceptives are then offered, most often female sterilization and rarely LARC. Control group female participants will be linked with ASHAs to support access to PHC FP services. ANMs will not provide LARC or GE counseling for control condition women. Men will receive no FP counseling.

**Timeline:** Phase 1 of the study preparation will take approximately 3 months. Phase 2 will be in month 4 to month 60, including enrollment and intervention start at month 4, 9 month follow up at month 13, and 18 month follow up at month 22. The outcome analysis will also be carried out in this phase at month 40. Phase 3, on sustaining the intervention, will overlap from month 7 to month 60.

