The primary analyses will use an intent-to-treat approach and analyze all subjects according to randomized group. For subjects missing month 9 or 18 endpoints, these will be multiply imputed from the lower (worse) half of the distribution from their arm (conservative approach). Additional analyses will be conducted using a per protocol approach that includes only those subjects who complete the full intervention. Analyses will use women's data only; however, men's data will be used to validate outcomes a) increased contraceptive use, and b) reduced unintended pregnancy. Exploratory analyses using outcomes of contraception by type (e.g., LARC) may be conducted if numbers are sufficient across time-points.

At 18 month follow-up, healthcare facilities in the study area will be surveyed to assess provision of FP counseling and methods, availability of FP methods, approximate FP method client volume, provider type/qualifications, and participation in the CHARM2 intervention. Healthcare facility location GPS will be collected for mapping of healthcare services in the study area; no personally identifying information regarding the providers will be collected.

At 18 month follow-up, participants' location data will be re-collected in the form of GPS coordinates; this data will be used to examine distances to healthcare facilities in the study area. GPS data will be collected in a separate survey form to be accessed only by NIRRH in-country study staff. In-country study staff may use this location data, in conjunction with healthcare facility location data, to calculate participant-level distance to healthcare providers. Geolocation data will **not** be shared with UCSD or any other external sources; any maps produced which visualize healthcare facility location and access will **not** include participant locations. Calculated distances **only** may be shared with UCSD analysts, to be summarized and utilized in adjusted regression models to better understand drivers of and barriers to health care services generally, and family planning services specifically, in the study area.

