## **15. RISK MANAGEMENT PROCEDURES AND ADEQUACY OF RESOURCES**

In addition to the protections against risks briefly outlined in the Potential Risks section above, additional precautions have been outlined to reduce risk for violence to wives, given the vulnerability of this population. These protocols and procedures were developed based on WHO guidelines for domestic violence research, and based on existing NIH-funded projects Drs. [name] and [name] have or have had in both India and the US. These protocols include (but are not limited to) the following efforts:

If women at any point in the study report life-threatening violence from husbands, these women will be withdrawn from the study and provided with supported referral (assistance with transport and accompaniment) to a state domestic violence agency (CEHAT) by research or program staff. Research staff, ANMs, and trained providers/counselors will be trained on how to work with women in these situations in accordance with WHO guidelines for domestic violence research. For example, this includes using "dummy" questions if privacy is breached during an interview or an ANM or trained provider/counselor visit, and training staff to identify when women are distressed and need debriefing or immediate health attendance. They will also offer support to conduct a safety plan with woman reporting spousal violence to ensure she has thought through ways to safely escape her situation should she choose to do so.

Research and program staff will never disclose to any family member who participated in the study, what questions were asked of them, or what responses were given. Participants will also be asked not to share the questions and their responses with others, particularly if they think it could put them at risk for abuse. This is in line with WHO procedures for domestic violence research.

Women will always be assessed for domestic violence in private places, with clarification that women can refuse to respond to items or questions, with supported referral and safety planning for identified victims, with validation that violence is never a woman's fault, with protocols and confirmation that all information provided is kept confidential, and with emotional debriefing subsequent to disclosure, in line with WHO procedures for domestic violence research.

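### The additional per-protocol analysis selects on completing the CHARM2 sessions, a criterion with no control-arm counterpart, so its contrast is not protected by randomisation and may be biased

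*Combined protocol and SAP*

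**What the plan says.** Section 9, Quantitative Data Collection, sets the main approach: "The primary analyses will use an intent-to-treat approach and analyze all subjects according to randomized group". As an additional analysis it then plans a "per protocol approach that includes only those subjects who complete the full intervention".

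The same section, under the CHARM2 intervention, describes two sessions for the husband, two for the wife and one for the couple: "The 5 sessions will be delivered across 3 months with a minimum of 1 week between the men's sessions". Under the control condition, "Control group female participants will be linked with ASHAs to support access to PHC FP services", and for husbands, "Men will receive no FP counseling".

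The plan does not say how many sessions count as completion, which controls enter the per-protocol comparison, or how selection into completion will be handled. The covariate-adjusted models under Data Analysis are a separate secondary analysis and are not tied to the completer set.

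**The concern.** A per-protocol rule needs a criterion that can be applied in both arms, or a method that allows for its absence in one. Here the criterion is attendance by both spouses at a course of sessions that only one arm is offered. Couples who finish the course may differ from those who do not in motivation to use contraception, in agreement between spouses and in exposure to marital violence. Controls of both kinds remain mixed together.

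What is at stake is how an additional result is interpreted. If the completer contrast is reported beside the intent-to-treat result without qualification, a reader may take it as the effect of actually receiving CHARM2. It would in fact combine any such effect with the difference between couples who complete and couples in general.

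**Working it through.** The plan gives no figure for the per-protocol set, so there is none to reproduce. The check sets the rule against the design and then illustrates the size of a possible bias.

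**Step 1: which controls could be compared.** Applied literally, the rule removes every control. The workable readings keep all controls, those followed up, or those linked to an ASHA. None of these selects controls on whether both spouses would have attended five sessions. On every reading, completion-based selection acts in the CHARM2 arm only.

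**Step 2: whether selection is plausible.** Of the earlier CHARM trial, Section 5 says "it demonstrated good participation from men (91%) but less from couples (51%), largely due to women's discomfort with a male provider". Participation there depended on characteristics of the woman and her circumstances. Section 15 adds a route tied to an outcome: "If women at any point in the study report life-threatening violence from husbands, these women will be withdrawn from the study". The withdrawal rule covers both arms. However, Section 14 says wives are asked about marital sexual violence within intervention sessions, which gives CHARM2 wives an extra occasion to disclose. A wife withdrawn before her last session leaves the completer set.

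**Step 3: size under no true effect.** Let *p* be follow-up contraceptive use in either arm, *c* the completion share, and *g* the gap in use between completers and non-completers. Then *p* = *c*·*p*_C + (1 − *c*)(*p*_C − *g*), so completers' use is *p*_C = *p* + (1 − *c*)*g*. The spurious difference from unselected controls is (1 − *c*)*g*.

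Inputs:
- *p* = 40%, the control rate expected in Section 9, Sample size considerations.
- *c* = 51% and 91%, the couple and male participation figures from the earlier trial, borrowed as assumptions; 80% is an assumed middle value.
- *g* = 5, 10 and 20 points, assumed because the documents give no gap.

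| Completion | 5-point gap | 10-point gap | 20-point gap |
|---|---|---|---|
| 51% | 0.49 × 5 = 2.5 | 0.49 × 10 = 4.9 | 0.49 × 20 = 9.8 |
| 80% | 0.20 × 5 = 1.0 | 0.20 × 10 = 2.0 | 0.20 × 20 = 4.0 |
| 91% | 0.09 × 5 = 0.5 | 0.09 × 10 = 0.9 | 0.09 × 20 = 1.8 |

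Check for 51% and 10 points: completers 44.9%, non-completers 34.9%, and 0.51 × 44.9 + 0.49 × 34.9 = 40.0. For scale, the plan's power calculation uses a difference of 12 points (40% against 52%).

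**Step 4: whether baseline differencing removes it.** Data Analysis includes baseline as a time point for contraception and marital sexual violence only, so unintended pregnancy gets no such correction. For the other two, if the same model were used and *g*₀ were the gap at baseline, the spurious difference in differences would be (1 − *c*)(*g* − *g*₀) on the risk-difference scale. A stable gap cancels; a gap that opens after baseline does not. For contraception, eligibility excludes consistent modern users in the previous three months. That compresses *g*₀, so much of any difference in motivation would appear only at follow-up.

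**Step 5: choice of exposure in a complier-average analysis.** With controls receiving no sessions, the estimate is the intent-to-treat difference divided by the share exposed. If the exposure is full completion, a 6-point intent-to-treat difference at 51% completion becomes 6 / 0.51 = 11.8 points. That figure credits the whole effect to completers. If partial attenders also benefited, it is too large.

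**The case against.** The strongest reply is that little rests on this analysis. Intent-to-treat is primary, the per-protocol analysis is labelled additional, and no hypothesis, power figure or stopping rule uses it. Data Analysis attaches its causal claim to the unadjusted primary analysis. All of that stands and limits the weight of the point.

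The illustration can also be challenged. The gaps are assumed. The 51% and 91% are participation figures from a different intervention, not five-session completion rates. CHARM2 adds female providers and a choice of home or clinic delivery to address the stated cause of low couple participation. This stands too: completion may be high, and the bias then small.

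Baseline differencing is a partial answer. It would absorb a stable baseline difference for two outcomes if applied to the completer set, but not later divergence, and it does not reach unintended pregnancy. Restricting controls to those followed up or linked to ASHAs would supply a comparator without matching the selection.

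Three stronger readings are tempting, and the documents do not support them.
- A reader might infer that the bias must favour CHARM2 on all three outcomes. That is plausible, but completers who start with less violence also have less room to improve, and nothing in the plan fixes the direction.
- A reader might infer that the completer result will drive the cost-effectiveness case. The Cost Effectiveness section refers to the outcome analyses without naming a population.
- A reader might infer that all controls will be the comparator. The plan does not say.

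**Conclusion.** The point holds for the additional per-protocol analysis only. As written, it either has no comparator or compares couples selected after randomisation with controls who are not selected in the same way. Nothing else in the plan repairs this. The contrast may be biased, probably towards CHARM2, but neither direction nor size can be established from the documents. The 4.9, 2.0 and 0.9 points for a 10-point gap show how the bias depends on completion; they are not forecasts. They assume no true effect, the stated gap, unselected controls and no baseline differencing. The primary intent-to-treat analysis is unaffected, so this is a correction that should be made and not a threat to the trial's main conclusion.

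**What to change.** Make the adherence analysis a complier-average causal effect estimate:
- allocated arm as the instrument;
- attendance at any session as the main exposure;
- all randomised couples kept in their allocated arm;
- standard errors at cluster level, with a small-sample correction for 20 clusters.

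Use full completion as the exposure only in a sensitivity analysis, with a note that it inflates the estimate if partial attendance has an effect. Write down what counts as attending and as completing. Confirm that attendance is recorded for each couple: the completer analysis already needs this, but the plan mentions only process and quality assurance data in general terms.

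If a completer analysis is still reported, state which controls it uses and label it a non-randomised comparison.

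The cost is SAP wording and one extra model. Intervals will be wider than those of the simple completer contrast. The estimate also assumes that allocation acts only through the sessions. Spillover could breach this if couples in CHARM2 clusters who attend nothing are influenced by neighbours who do, and the report should say so.

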## **Qualitative Data Collection:**

In-depth interviews with CHARM2 providers and participants, as well as control condition couples, described as part of Aim 3, will assess perceived outcomes of the intervention, for triangulation with quantitative findings.

At 9 month follow-up, a subsample of CHARM2 couples (n=50 couples; 5 per CHARM2 intervention cluster) will be randomly selected to participate in IDI to assess how the program altered their relationship and behaviors, including FP, MSV and sexual communication. Interviews will be 45-60 minutes in length and conducted in Marathi. Interview participation may influence responses at 18 month follow-up but delaying qualitative feedback to 18 month follow-up may affect participant recall. Thus, we will compare these individuals at 18 month follow-up with those intervention participants who did not participate in interviews, and if significant differences are seen, we will drop them from further analyses. MILs of couples (mother's of the young married men) that participate in IDIs will also be invited for interviews *only* through the couples themselves, and with the couples knowledge that we will be describing the CHARM2 intervention to them. FGDs with MILs will assess family dynamics of young couples with regard to husband's parents, family planning attitudes, and their perceptions of the CHARM2 program.

All CHARM2 providers (n=20 providers/ANMs/counselors) will be asked to participate in IDIs to assess their perceptions of CHARM2 quality, acceptability and utility. NIRRH staff will conduct the 30 minute open-ended interviews with providers. As is standard in India, no monetary incentives will be offered.

At 18 month follow-up, a subsample of control condition couples (n=20 couples, 2 per control cluster) will be randomly selected to participate in IDI to understand FP counseling and access and gender-based violence in the study area outside of the CHARM2 intervention.

**Data Analysis:** The primary comparison of the binary outcomes between intervention groups at 9 & 18-months will use mixed-effects longitudinal logistic regression, with random effects for the individual (couple) and for geographical clusters, over time. Baseline will be included as a time point (Aims 2a, 2b only). A categorical time effect will be used (profile model). A “difference-in-differences” analysis will compare the treatment arms. Statistically, this amounts to testing for an interaction between time and treatment arm in the longitudinal model. In addition, the intervention groups will be compared via a generalized estimating equations (GEE) logistic regression analysis. The GEE models will use a nested exchangeable working correlation matrix that takes into account geographic clusters and the individual (couple) within the cluster. No other covariates will be included in the primary analysis. Since the treatment assignment is at random this “un- adjusted” analysis will provide a causal effect of the intervention. However, we will also conduct secondary analyses, adjusting for potentially relevant covariates (e.g., age, current pregnancy, past year child- birth, etc.), in addition to time and treatment arm, using backward model selection at the  $\alpha=0.15$  threshold level. These secondary analyses may improve precision (power) of estimating the treatment effect and reduce any bias due to random imbalances between arms.

**Implementation Science:** Subsequent to the efficacy trial, brief (30-60 minute) IDI with key stakeholders (n = 50) from FP and rural and public health at multiple levels (local, state, national, international) will be conducted, as will a cost-effectiveness analysis of CHARM2. IDI stakeholder participants will be identified by community leaders and advisors at multiple levels, including the villages in which the study will be undertaken, the District Health Office partnering with us for this study, and the Technical Advisory Committee who will guide and support our proposed work. NIRRH research staff will contact stakeholders via phone or email, to conduct the 30 minute interviews in English, Hindi or Marathi in-person or via phone, to share CHARM2 approach/findings and to ask whether and how this could be used to support FP programming in rural India. Interviews will be audio recorded unless the participant refuses, in which case detailed notes will be taken. Transcripts will be saved as text documents and imported into ATLAS.ti®, software that helps to organize and facilitate analysis of qualitative data. [name] will guide data analysis using a grounded theory approach, in which there is a continuous interplay between data collection and analysis to iteratively generate themes and adapt interview guides. Analysis will be initiated upon completion of the first wave of data collection, by site, using the following approach: (1) Data Immersion- [name] and the research staff will read and reread transcripts and associated field notes to familiarize themselves with the narratives and create memos to guide theme development; (2) Theme Generation- the team will develop a list of emergent key themes seen across narratives; (3) Framework Development- themes and their intersections will be reviewed and discussed with the investigator team to create a framework to understand the issues of focus; revisions to protocols or extensions of data collection may result in order to better support framework creation; (4) Codebook Development- a codebook will be developed based on the framework themes and any resultant subcodes, to guide further data analysis; and (5) Coding and Iterative Analysis- two coders will code and analyze all data using themes generated in steps 2-4. Coders will code separately and codes will be analyzed for inter-coder reliability based on Cohen’s Kappa. Coding discrepancies will be reviewed to reach consensus. If new codes are identified, the codebook will be expanded, and data will be re-coded. Additional participants may be recruited to reach saturation.

**Cost Effectiveness:** To further inform utility of CHARM2, a cost-effectiveness analysis will be conducted under the direction of [name] using WHO-CHOICE methodology, an internationally accepted standard of economic analysis of health programs. Costs will be collected prospectively and include capital costs (e.g., equipment, space) and recurrent inputs (e.g., FP supplies, administrative costs). Given an expected outcome of improved contraception, costs of increases in non-CHARM2 FP services will be included as partner costs. Costs will be discounted at a rate of 3% per year, per WHO-CHOICE recommendations, varying from 0% to 6% in the sensitivity analysis. Drivers of variation in the total program cost will be assessed using multivariate linear regression. Cost-effectiveness will be calculated by dividing the total program costs by total health outcomes achieved over intervention duration. Outcome measures will include number reached by the CHARM2 and unintended births averted (based on outcome analyses). Based on prior research, we will use an estimate of 3.8 DALYs averted per unintended birth averted. We will also include quantitative measurements of other benefits from unintended pregnancy prevention (e.g., household savings and assets) to capture some of the spill over effects of when unintended pregnancies are prevented. Following WHO benchmarks, the intervention will be categorized as ‘very cost-effective’ if the cost per DALY averted is  $<1x$  the country’s per capita GDP. We will undertake a probabilistic sensitivity analysis, sampling each cost and outcome from an appropriate distribution to determine mean incremental cost-effectiveness, and assess drivers of uncertainty using ANCOVA. Findings will be used to support sustainability and scale up of CHARM2 for use in rural India and elsewhere.

**Sample size considerations:** Treatment effects detectable with 80% power given the 2-armed design with 20 clusters of 48 measurable couples (assuming 80% retention) per arm, or n=960 observed couples. Power calculations took into account multiple levels of clustering, both within-village and within-sub center variance.

- a) Based on CHARM, we expect the proportion of women using modern contraception in the control group to be 40% at 18 month follow-up. This study will have 83.3% power to detect an absolute difference of 12% or more between treatment groups at follow-up, or 40% vs 52% in the two groups, with total kappa [variance]=0.10, assumed to be split equally between within-village variance and within-cluster variance . These values were found in the CHARM study.
- b) Based on CHARM, we expect that 89.2% of women in the control group will report no recent MSV at 18 month follow-up. We have 91.5% power to detect an absolute difference of 6% or more between treatment groups (89.2% vs. 95.2%) with kappa=0.036,

assumed to be split equally between within-village variance and within-cluster variance. The effect size of 6% difference and the kappa=0.036 were observed in the CHARM study.

c) Based on CHARM, we expect the proportion of women with no unintended pregnancy over 18 month follow-up to be 90% in the control group. This study will have 89.5% power to detect an absolute difference of 5.5% or more between groups (90% vs. 95.5%), with kappa=0. The effect size of 5.5% difference is based on a meta-analysis of cluster RCTs evaluating impact of FP interventions on unintended pregnancy (with comparable measures to this study). The study showed a 50% reduced risk for intervention participants with no unintended pregnancy in the CHARM group, or 5.5%. The kappa=0 is based on the CHARM study, where no significant intra-cluster correlation was found for this outcome.

While we will use longitudinal mixed effects logistic regression methods in our analyses, for power calculations we considered only the 18-month time point in a model similar to those to be used in the analyses. Power for the prescribed longitudinal analyses will be higher. Power calculations for each hypothesis used statistical simulations with 10,000 iterations. The conversion from kappa to the random cluster effect was done using the delta method, and was confirmed through the simulation.

